1.2 OBJECTIVES

1.2.1 Part 1: Dose escalation phase

1.2.1.1 Primary objectives

To determine the safety and tolerability of 4, 8, and 15 mg of GZ/SAR402671, as compared to placebo, when administered orally daily for 4 weeks in early-stage PD patients carrying a GBA mutation or other prespecified sequence variants (from now on both mutation types are referred to as ‘GBA mutation’). This will allow selection of the dose for the second part of this study (this does not apply to Japanese patients).

1.2.1.2 Secondary objectives

To assess the PK profile of daily oral dosing of GZ/SAR402671 in plasma when administered at doses of 4, 8, or 15 mg over a 4-week period in early-stage PD patients carrying a GBA mutation.

To assess the exposure of GZ/SAR402671 in CSF when administered at doses of 4, 8, or 15 mg over a 4-week period in early-stage PD patients carrying a GBA mutation.

1.2.1.3 Exploratory objectives

To assess the pharmacodynamic response of daily oral dosing of GZ/SAR402671 in plasma and CSF when administered at doses of 4, 8, or 15 mg over a 4-week period, as measured by GL-1 in early-stage PD patients carrying a GBA mutation.

To explore the effect of GZ/SAR402671 on scores from selected scales and questionnaires which will be used in this study over an 8 week period in early-stage PD patients carrying a GBA mutation.

1.2.2 Part 2: Treatment phase

1.2.2.1 Primary objectives

To determine the efficacy of GZ/SAR402671 in patients with early-stage PD carrying a GBA mutation when administered orally daily at the dose selected in Part 1, over a 52-week period, as compared to placebo.

1.2.2.2 Secondary objectives

To demonstrate the overall safety and tolerability of GZ/SAR402671 administered orally daily for 52 weeks in early-stage PD patients carrying a GBA mutation as compared to placebo.

To assess the pharmacodynamic response to daily oral dosing of GZ/SAR402671 in plasma and CSF as measured by GL-1 in early-stage PD patients carrying a GBA mutation over a 52-week period.

1.2.2.3 Exploratory objectives

To explore the effect of GZ/SAR402671 on scores from selected scales and questionnaires which will be used in this study. Of note, for patients receiving levodopa or other PD medication, assessment of scales and questionnaires will be performed during the OFF state (ie, no PD medication may be taken for at least 12 hours prior to the efficacy assessments) except for the Hoehn & Yahr (H&Y) scale which will be completed in "ON" state only at baseline visit (see inclusion criteria I 05).

To assess the effect of GZ/SAR402671 on neurologic functional status via functional neuroimaging over a 52-week period.

To assess the PK profile of GZ/SAR402671 in plasma and CSF of early-stage PD patients carrying a GBA mutation.

To evaluate the pharmacodynamic response to GZ/SAR402671 in plasma and CSF as measured by glucosylsphingosine (lyso-GL-1) in early-stage PD patients carrying a GBA mutation.

To explore the effect of GZ/SAR402671 on CSF biomarkers related to PD or neurodegeneration, including total α -synuclein (α -Syn), neurofilament light chain (NFL), tau, phospho-tau, as well as beta-amyloid (1-40 and 1-42).

1.3 DETERMINATION OF SAMPLE SIZE

1.3.1 Part 1: Dose escalation phase

As Part 1 is an exploratory, dose-escalation study, the sample size is not based on the statistical power calculation. Each cohort (for non-Japanese patients only) will have a 4:1 randomization ratio, and the total sample size will be approximately 15 patients (including 12 on GZ/SAR402671 and 3 on placebo).

For Japanese patients only, each cohort will have a 3:1 randomization ratio, and the total sample size will be approximately 12 Japanese patients (including 9 on GZ/SAR402671 and 3 on placebo). This sample size in Japanese Part 1 is considered based upon empirical and feasibility considerations.

Therefore, the total sample size in Part 1 will be approximately 27 patients.

Patients who do not complete a minimum number of scheduled doses of study drug in Part 1 and withdraw for reasons other than safety may be replaced.

1.3.2 Part 2: Treatment phase

Approximately 216 PD patients carrying a GBA mutation in total will be randomized in a 1:1 ratio to the GZ/SAR402671 or placebo groups. A sample size of 108 patients for the GZ/SAR402671 group and 108 for the placebo group provides at least 80% power to detect a 4.06

points improvement compared to the placebo mean change in MDS-UPDRS Parts II+III score over 52 weeks. This sample size calculation assumes a 2-sided $\alpha = 0.05$, a standard deviation for the change from baseline to Week 52 in MDS-UPDRS Part II+III of 10.01 points (estimated from the Parkinson's Progression Markers Initiative [PPMI] database), and allows for an approximate 10% early terminations/unevaluable patients.

A previous study showed that a 3.25 points difference on MDS-UPDRS Part III represent the minimal clinically important difference (MCID) for detecting an improvement. It was estimated from the PPMI database that the standard deviation for change from baseline to Week 52 in MDS-UPDRS Part III was 8.01 points; therefore the MCID of 3.25 points would represent an effect size of 0.406. Since no study evaluated the MCID for MDS-UPDRS Part II+III, the same effect size of 0.406 was assumed, resulting in an estimated MCID of 4.06 points, using the standard deviation of 10.01 for change from baseline to Week 52 in MDS-UPDRS Part II+III also estimated from the PPMI database.

[figure not shown]
Of note, the approximate 27 (12 Japanese and 15 non-Japanese) early-stage PD patients carrying a GBA mutation from Part 1 may be re-randomized and participate in all of the assessments in Part 2 of this study; however, they will not contribute to the primary efficacy, safety, PK and pharmacodynamics analyses, and will be described separately.

Calculations were made using nQuery 7.0 Advisor software.

1.4 STUDY PLAN

The following figures present the graphical study design:

[figure not shown]
Figure 1 - Graphical study design for Part 1

Abbreviations: CSF: cerebrospinal fluid; LP: lumbar puncture; max: maximum; MDS-UPDRS: Movement Disorder Society-Unified Parkinson's Disease Rating Scale; N: number of subjects; PO: oral; qd: once daily; R: randomization.

** The LP may be done during the screening period within 14 days prior to randomization (Day -14 to Day -1) or on the day of randomization (Day 1 predose). Only 1 sample will be collected, during screening or at Day 1.

Figure 2 - Graphical study design for Part 2

Abbreviations: R: randomization; W: weeks; max: maximum; CSF: cerebrospinal fluid; pts: patients; LP: lumbar puncture.

- The LP may be done during the screening period within 14 days prior to randomization (Day -14 to Day -1) or on the day of randomization (Day 1 pre-dose). Only one sample will be collected, during screening or at Day 1.
- The dose of GZ/SAR402671 will be determined in Part 1.

Abbreviations: CSF: cerebrospinal fluid; LP: lumbar puncture; max: maximum; N: number of patients; PO: oral; qd: once daily; R = randomized; W = weeks.

* The LP may be done during the screening period within 14 days prior to randomization (Day -14 to Day -1) or on the day of randomization (Day 1 pre-dose). Only 1 sample will be collected, during screening or at Day 1; LP at baseline will not be required to confirm eligibility of patients from Part 1 to enroll in Part 2.

** The dose of GZ/SAR402671 will be determined in Part 1.

1.5 MODIFICATIONS TO THE STATISTICAL SECTION OF THE PROTOCOL

This section summarizes major changes to the protocol statistical section with emphasis on changes after study start (after the first patient was enrolled).

The protocol history table below gives the timing, rationale, and key details of major changes to the protocol statistical section.

Table 1 - Protocol amendment statistical changes

Amendment Number	Rationale	Description of statistical changes
1	Inclusion of a Japanese cohort	Increase in sample size of Part 1 (12 additional Japanese patients) Definition of specific Japanese populations for efficacy, safety, PK and pharmacodynamics analyses. Separate analyses for Japanese and non-Japanese patients
3	Incorporate feedback received from Health Authorities in the United States and Japan	Clarification that patients from Part 1 who are re-randomized in Part 2 will not be included in Part 2 analyses (for efficacy, safety, pharmacokinetics and pharmacodynamic analyses). These data will be described separately.
4	Removal of interim analysis	Interim analysis planned for administrative purposes that are no longer required by the Sponsor.

1.6 STATISTICAL MODIFICATIONS MADE IN THE STATISTICAL ANALYSIS PLAN

The statistical analysis plan history table below gives the timing, rationale, and key details for major changes to the statistical analysis features in the statistical analysis plan.

Table 2 - Statistical analysis plan changes

SAP version number	Date approved	Rationale	Description of statistical changes
1	18-Dec-2017	Initial version	-
1	25-Apr-2018	Specification of an analysis of Part 1 data after completion of Part 1 (non-Japan)	An analysis of Part 1 (non-Japan) data will be performed when all non-Japanese patients have completed Part 1, and after a two-step database lock (see Section 3.4 and Section 5).
1	30-Nov-2018	Specification of an analysis of Part 1 data after completion of Part 1 (Japan)	An analysis of Part 1 (Japan) data will be performed when all Japanese patients have completed Part 1, and after a two-step database lock (see Section 3.4 and Section 5). Update of the EQ-5D-5L scoring algorithm (see Appendix H) Inclusion of the procedure for internal data review as appendix of the SAP (Appendix K)
1	22-Jul-2020	Specification of analyses of Part 2 data	Description of analyses planned for Part 2 of the study.
2	This version	Comment from FDA on version 1, received on 16-Oct-2020 and 17-Nov-2020, to exclude data collected after treatment discontinuation from the primary analysis and use them in sensitivity analyses. Delayed visits due to COVID-19 pandemic situation	Change in primary and secondary estimand (Section 2.4.4.1) Exclusion of data collected after premature treatment discontinuation from the primary efficacy analysis (Section 2.4.4.1) Addition of a sensitivity analysis including data collected after treatment discontinuation (Section 2.4.4.1) Exclusion of data after premature treatment discontinuation from analysis of secondary efficacy endpoints (Section 2.4.4.2) and exploratory efficacy endpoints (Section 2.4.4.3) Analysis window of Week 52 visit extended to D570 (Section 2.5.4 , Table 6)

2 STATISTICAL AND ANALYTICAL PROCEDURES

2.1 ANALYSIS ENDPOINTS

2.1.1 Demographic and baseline characteristics

The baseline value is defined as the last available value obtained before or equal to the date and time of the first double-blind Investigation Medicinal Product (IMP) administration. In case of missing time of the first double-blind IMP administration and/or time of assessment, the baseline value is defined as the last available value obtained before or equal to the date of the first double-blind IMP. For patients randomized and not treated, the baseline value is defined as the last available value obtained before or equal to the date and time of randomization.

All baseline safety and efficacy parameters are presented along with the on-treatment summary statistics in the safety and efficacy sections ([Section 2.4.5](#) and [Section 2.4.4](#)).

Demographic characteristics

Demographic variables include:

- Gender (Male, Female)
- Age in years (quantitative and categorical variable : <45, [45 – 65[, [65 - 75[and ≥75 years),
- Race (White, Black or African American, Asian, American Indian or Alaska Native, Native Hawaiian or other Pacific Island, other)
- Ethnicity (Hispanic, non-Hispanic)
- Weight in kilograms (quantitative and categorical variable: <50, ≥50 and <100, ≥100)
- Body mass index (BMI) in kg/m² (quantitative and categorical variable: <30, ≥30)

Parkinson's disease history

Parkinson's disease history include:

- Time since onset of symptoms (in years)
- Time since diagnosis (in years)
- Predominance of symptom at onset (Tremor, Rigidity / Bradykinesia)
- Family history of Parkinson's disease (yes, no)

Any technical details related to computation, dates, and imputation for missing dates are described in [Section 2.5.3](#).

GBA mutations

GBA mutations will be categorized as severe GBA mutation or other GBA mutation. The list of most common mutations is provided in Appendix B.

Medical or surgical history

All medical or surgical history information in the e-CRF will be coded using the version of Medical Dictionary for Regulatory Activities (MedDRA) currently in effect at Sanofi at the time of database lock.

Alcohol Habits

Alcohol habits include:

- Frequency of alcoholic drinks in the last 12 months (Never/Occasional/At least monthly/At least weekly/At least daily)
- Number of standard drinks (1 or 2/Greater than 2, where standard drink means 1 pint/bottle of beer, 1 glass of wine, 1 shot of hard liquor...) per day when drinking alcohol

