2.4.5 Analyses of safety data

Safety analyses will be performed on the safety populations (see [Section 2.3.2](#)), separately for Part 1 and Part 2 of the study. In Part 1, data will be presented separately for Japanese and non-Japanese patients.

In Part 2, safety data will be presented separately for the two following periods:

- Safety analysis of the 52-week blinded treatment period of Part 2. This analysis will present safety data collected up to the Week 52 visit (or end of treatment visit in case of premature treatment discontinuation before Week 52). Safety analyses will present safety data from the two treatment arms:
 - Placebo
 - GZ/SAR402671 15mg

- Safety analysis of the 104-week long-term follow-up period of Part 2. This analysis will present safety data collected from the Week 52 visit to the end of study, excluding the initial 52-week blinded treatment period. Only patients having received GZ/SAR402671 15mg during the long-term follow-up period will be included in this analysis. Safety analyses will present safety data from the following groups:
 - Delayed start: patients having received placebo during the 52-week treatment period, then having received GZ/SAR402671 during the long-term follow-up period.
 - Early start: patients having received GZ/SAR402671 during the 52-week treatment period, then having continued to receive GZ/SAR402671 during the long-term follow-up period.
 - All patients: all patients having received GZ/SAR402671 during the long-term follow-up period
- Safety analysis of the overall GZ/SAR402671 treatment period in Part 2. This analysis will present all safety data collected from the first intake of GZ/SAR402671 in Part 2 to the last intake of GZ/SAR402671 in Part 2 plus 6 weeks. All patients having received GZ/SAR402671 15mg in Part 2 (either during the 52-week blinded treatment period or during the long-term follow-up period) will be included in this analysis. Safety analyses will present safety data from the following group:
 - Overall GZ/SAR402671: patients having received GZ/SAR402671 during the 52-week treatment period and/or during the long-term follow-up period.

Details of timing of these two analyses is presented in [Section 4](#).

General common rules

The safety analysis will be conducted according to the Sanofi document BTD-009536 (version applicable at the time of database lock) “Analysis and reporting of safety data from Clinical Trials through the Clinical Study Report.”

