All safety analyses will be performed using the following common rules:

- Safety data in patients who do not belong to the safety population (eg, exposed but not randomized) will be listed separately.
- The baseline value is defined in [Section 2.1.1](#)
- The potentially clinically significant abnormality (PCSA) values are defined as abnormal values considered medically important by the Sponsor according to predefined criteria/thresholds based on literature review and defined by the Sponsor for clinical laboratory tests, vital signs, and ECG (PCSA version dated 24 May 2014 [[Appendix A](#)])
- PCSA criteria will determine which patients had at least 1 PCSA during the TEAE period, taking into account all evaluations performed during the TEAE period, including unscheduled or repeated evaluations. The number of all such patients will be the numerator for the on-treatment PCSA percentage

- The treatment-emergent PCSA denominator by arm for a given parameter will be based on the number of patients assessed for that given parameter in the TEAE period by treatment arm on the safety population
- For quantitative safety parameters based on central laboratory/reading measurements, descriptive statistics will be used to summarize results and change from baseline values by time point and treatment arm. Summaries will include the endpoint baseline value, the last on-treatment value and change from baseline, the worst on-treatment value and change from baseline. The last on-treatment value is commonly defined as the last value collected during the treatment period (see [Section 2.1.4](#)). The worst on-treatment value is defined as the nadir and /or the peak post-baseline during the treatment period according to the direction (minimum or maximum) of the abnormality as defined in the PCSA list
- All measurements (scheduled or unscheduled) will be re-allocated as given in [Section 2.5.4](#), [Table 3](#) and [Table 6](#) and re-allocated visits measurements will be included in the by-time point summary
- The analysis of the safety variables will be essentially descriptive and no systematic testing is planned

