2.5.4 Windows for time points

Data analyzed by time point (including efficacy, laboratory safety data, ECG, vital signs, quality of life and PK concentration) will be summarized using the analysis windows given in [Table 3](#), [Table 4](#), [Table 5](#), [Table 6](#) and [Table 7](#)). These analysis windows will be applicable for all analyses, and they are defined to provide more homogeneous data for time point-specific analyses.

For efficacy and quality of life endpoints, D1 will be defined as the day of randomization. For safety endpoints, D1 will be defined as the day of first IMP intake. In Part1, in case of treatment interruption of at least 7 days (corresponding to approximately 5 half-lives) between the day of first IMP intake and subsequent IMP intakes, D1 will be defined as the day of IMP resumption after treatment interruption (both for efficacy and safety endpoints).

Table 3 - Analysis windows definition for Part 1 - All endpoints except ECG and PK

Time point	Targeted study day	Analysis window in study days
Week 0 / Day 2	D2	D2
Week 0 / Day 3	D3	D3
Week 2	D15	D8 to D21
Week 4 ^a	D29	D22 to D42
Week 8	D57	D43 to D70
Week 12	D85	D71 to D98
Week 16	D113	D99 to D126
Week 20	D141	D127 to D154
Week 24	D169	D155 to D182
Week 28	D197	D183 to D210
Week 32	D225	D211 to D238
Week 36	D253	D239 to D266
Week 40	D281	D267 to D294
Week 44	D309	D295 to D322
Week 48	D337	D323 to D350
Week 52	D365	D351 to D378

^a For vital signs, any data collected between D22 and D42 will be further assigned to analysis window "Week 4 / Day 1" or "Week 4 / Day 2" as per eCRF page.

Table 4 - Analysis windows definition for Part 1 – ECG

Time point	Target study day	Analysis window
Day 1 / Pre-dose	Day 1 / Pre-dose	Before Week 0/Day 1 dose
Day 1 / 2 hours post dose	Day 1 / 2 hours post dose	1h to 2h59 after Week 0/Day 1 dose
Day 1 / 4 hours post dose	Day 1 / 4 hours post dose	3h to 4h59 post-dose after Week 0/Day 1 dose
Day 1 / 6 hours post dose	Day 1 / 6 hours post dose	5h to 8h post-dose Week 0/Day 1 dose
Week 4	D29	D22 to D42
Week 28	D197	D183 to D210

Table 5 - Analysis windows definition for Part 1 - PK concentration

Time point	Target study day	Analysis window
Day 1 / Pre-dose	Day 1 / Pre-dose	Before Week 0/Day 1 dose
Day 1 / 1 hour post dose	Day 1 / 1 hour post dose	0h50 to 1h10 after Week 0/Day 1 dose
Day 1 / 2 hours post dose	Day 1 / 2 hours post dose	1h45 to 2h15 after Week 0/Day 1 dose

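### In the pooled GZ/SAR402671 safety columns, delayed-start patients are measured from a baseline taken before their 52 placebo weeks, so placebo-year change is mixed with on-drug change

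*SAP*

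**What the plan says.** Section 2.1.1 ties baseline to the first double-blind dose, whichever product that dose contains: "The baseline value is defined as the last available value obtained before or equal to the date and time of the first double-blind" IMP administration.

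Section 2.4.5 opens its general rules with "All safety analyses will be performed using the following common rules". One of those rules reads "The baseline value is defined in" Section 2.1.1, and no exception follows.

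The same section defines three Part 2 safety analyses. Two of them include patients who began on placebo:

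- The follow-up analysis covers "safety data collected from the Week 52 visit to the end of study, excluding the initial 52-week blinded treatment period". It has a delayed-start group ("patients having received placebo during the 52-week treatment period, then having received GZ/SAR402671 during the long-term follow-up period"), an early-start group, and an All patients group that pools them.
- The Overall GZ/SAR402671 analysis covers "all safety data collected from the first intake of GZ/SAR402671 in Part 2 to the last intake of GZ/SAR402671 in Part 2", plus 6 weeks, in a single group.

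Section 2.5.4 sets the study-day origin: "For safety endpoints, D1 will be defined as the day of first IMP intake". The only reset it provides is for treatment interruptions of at least 7 days in Part 1. No Week 52 baseline or pre-GZ/SAR402671 baseline is defined anywhere in the SAP.

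**The concern.** Both analyses restrict the data window to the period on active drug, but the reference value stays at the start of the blinded period. For early-start patients the two coincide. For delayed-start patients they are a year apart, and whatever happened in that year on placebo is carried into the tabulated change.

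The overall table is the SAP's only pooled presentation of all Part 2 exposure to the drug, and it has no concurrent control. A reader will take its changes from baseline as changes on GZ/SAR402671. Drift during the placebo year could create an apparent change or hide a real one, and nothing in the table would show which. The SAP does start a separate clock for exposure: Section 2.4.3.1 calculates GZ/SAR402671 duration separately for placebo patients who switch. The missing second baseline therefore looks like an omission rather than a choice.

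**Working it through.** The plan states no figure on this point, so there is none to reproduce. The check traces the definitions and computes how much placebo time enters.

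**Inputs**

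- Baseline rule: Section 2.1.1, applied through the common rules in Section 2.4.5.
- Placebo duration in the delayed-start group: 52 weeks (Section 2.4.5).
- Follow-up time points: Weeks 78, 104, 130 and 156 (Section 2.5.4, Table 6).
- Assumption: the switch to active drug happens at the nominal Week 52. If a patient stayed on placebo until a late Week 52 visit, the placebo share would be larger.

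**Step 1: share of the interval spent on placebo.** At visit week w, a delayed-start patient has had w − 52 weeks of drug, while the tabulated change spans w weeks. The placebo share is 52 / w.

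| Visit week w | Weeks on drug (w − 52) | Placebo share, delayed start | Placebo share, early start |
|---|---|---|---|
| 78 | 26 | 52/78 = 66.7% | 0% |
| 104 | 52 | 52/104 = 50.0% | 0% |
| 130 | 78 | 52/130 = 40.0% | 0% |
| 156 | 104 | 52/156 = 33.3% | 0% |

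**Step 2: what enters the pooled mean.** Let B be the Section 2.1.1 baseline, G the last value on or before first GZ/SAR402671 intake, and X the on-drug value. Then X − B = (X − G) + (G − B). The first term is on-drug change and the second is placebo-year change. For early-start patients G = B, so the second term is zero. If a fraction p of the pooled patients are delayed-start, the pooled mean contains p × mean(G − B) that is not on-drug change. The number entering follow-up is not given. Randomization is 1:1, so p = 0.5 is a reasonable centre. For p from 0.4 to 0.6, 40% to 60% of the mean placebo-year change enters the pooled mean. The same extra term enters the last and worst on-treatment changes.

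**Step 3: which outputs use baseline.**

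- By-visit, last and worst changes (Section 2.4.5).
- Change-based PCSA criteria in Appendix A: creatinine (30% and 100% change), hemoglobin (decrease of 20 g/L or more), heart rate, systolic and diastolic blood pressure, PR, QRS and QTc increase.
- The split of PCSAs into normal/missing and abnormal at baseline (Sections 2.4.5.3 to 2.4.5.5).
- The count of BDI-II worsening (Section 2.4.5.9).

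For example, take a delayed-start patient whose hemoglobin fell by 20 g/L during the placebo year and then stayed level. Here G − B = −20 and X − G = 0, yet the patient meets the criterion in the GZ/SAR402671 column. Likewise, an abnormality that arose on placebo and persists is shown as an on-drug PCSA in a patient who was normal at baseline.

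**Step 4: study day.** D1 is first IMP intake, so in the row for week w of the overall table early-start patients have w weeks on drug and delayed-start patients have w − 52. The gap is 52 weeks in every shared row.

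**The case against.** Four arguments limit the point.

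- **The delayed-start column is labelled.** It is defined as placebo followed by drug, and aligning randomized groups on study week is legitimate in a delayed-start design. This stands. A reader might infer that every follow-up table misattributes placebo change to the drug. In the separate delayed-start column the sequence is visible, so the clear error lies in the pooled columns.
- **Lens opacity and weight.** Lens opacity is an event of special interest, so a reader might infer that its results are directly distorted. Section 2.4.5.8 reports worsening by central reader and does not tie it to the Section 2.1.1 baseline. A reader might also try to count false weight PCSAs. Weight is absent from the vital signs listed in Section 2.1.4.4, its appearance in a generic Appendix A list does not show that a table is planned, and the SAP gives no variability from which to count. No claim is made for either.
- **The summaries are descriptive.** Section 2.4.5 plans no systematic testing, and the randomized 52-week comparison is untouched. This limits the consequence but does not remove the error.
- **A sponsor standard also governs safety reporting.** Section 2.4.5 cites BTD-009536, of which only the PCSA list is shown. Whatever it says about extension periods, the SAP's explicit rule covers all safety analyses. If the standard differed, the two would need to be reconciled.

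**Conclusion.** The point holds for the All patients column of the follow-up analysis and for the Overall GZ/SAR402671 analysis. Followed as written, the plan measures on-drug change in delayed-start patients from before a 52-week placebo period and pools it with change measured from a true pre-drug value. The placebo shares in Step 1 rest only on the documents and a nominal Week 52 switch. The effect on any given parameter depends on its placebo-year change, which the SAP does not give, so no number of misclassified patients can be stated.

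Adverse event incidence and PCSA counts on absolute thresholds alone do not use a baseline value, apart from the baseline-status split. The primary efficacy conclusions are not involved. The change is worth making before the follow-up and overall tables are programmed, but it does not threaten the trial's main result.

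**What to change.** In Section 2.4.5, add a second safety baseline for delayed-start patients: the last value on or before first GZ/SAR402671 intake. Use it in the Overall GZ/SAR402671 analysis, in the All patients column of the follow-up analysis and, for consistency, in the delayed-start column. Keep the Section 2.1.1 baseline for the 52-week placebo-controlled analysis and for early-start patients, for whom it already precedes the drug.

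In Section 2.5.4, state that D1 in the overall analysis is the day of first GZ/SAR402671 intake. The existing Table 6 windows still work. With the switch on D365, the new day is the old day minus 364, so the target days 547, 730, 911 and 1095 become 183, 366, 547 and 731. These fall in the Week 26, 52, 78 and 104 windows.

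The cost is one extra baseline and study-day derivation, with no new data. Delayed-start patients will then have different baselines in different analyses, so each table needs a footnote naming the one used.

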Week 26 / within 2 to 4 hours post dose	D183 / within 2 to 4 hours post dose	Week 26/Day 1 - 1h45 to 4h30 after Week 26/Day 1 dose
Week 52 / Pre-dose	D365 / Pre-dose	Week 52 - Before Week 52 / Day 1 dose
Week 52 / within 2 to 4 hours post dose	D365 / within 2 to 4 hours post dose	Week 52/Day 1 - 1h45 to 4h30 after Week 52/Day 1 dose

If multiple valid values of a variable exist within an analysis window, the value collected at the scheduled visit will be used if within the analysis window. Otherwise the nearest from the targeted study day or time will be selected. If the difference is a tie, the value after the targeted study day or time will be used

For all endpoints except ECG at Day 1 and PK, if multiple valid values of a variable exist within a same day, then the first value of the day will be selected when time is available, else the scheduled visit will be selected.

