2.5.5 Unscheduled visits

For all analyses, unscheduled visit measurements may be used to provide a measurement for a time point, a baseline, if appropriate according to their definitions.

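### If a clock time is missing, the Section 2.1.1 fallback can make a post-dose Day 1 ECG the baseline of a Part 1 patient

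*SAP*

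**What the plan says.** SAP Section 2.1.1 gives two rules for treated patients.

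- With times known, baseline is the "last available value obtained before or equal to the date and time of the first double-blind Investigation Medicinal Product (IMP) administration". This excludes anything measured after dosing.
- Where the clock time of first dosing or of the measurement was not recorded, a date-only fallback applies: "the baseline value is defined as the last available value obtained before or equal to the date of the first double-blind IMP". Here the whole calendar day of first dosing qualifies.

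Section 2.5.4, Table 4, gives the Part 1 ECG time points on Day 1 as pre-dose and 2, 4 and 6 hours post-dose. The last has the window "5h to 8h post-dose Week 0/Day 1 dose". The later ECG time points are Week 4 and Week 28.

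Section 2.5.4 also has a rule for several values on one day, which picks the earliest timed value. Its scope leaves out Day 1 ECGs: "For all endpoints except ECG at Day 1 and PK, if multiple valid values of a variable exist within a same day". Section 2.5.5 adds that "unscheduled visit measurements may be used to provide a measurement for a time point, a baseline", where the definitions allow, and sets no pre-dose limit.

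Section 2.4.5 takes the safety baseline from Section 2.1.1. Section 2.4.5.5 summarises ECG changes from baseline and potentially clinically significant abnormalities (PCSAs). In Appendix A some ECG criteria use change from baseline: a QTc increase of more than 30 and up to 60 ms or of more than 60 ms, heart-rate changes of at least 20 bpm, and PR and QRS increases of at least 25%.

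**The concern.** The fallback drops the condition that the value precede dosing but still takes the last value. On a day with repeated ECGs, that is the one furthest after the dose. The rule is explicit, so a programmer following it literally would produce this baseline without any error in the code.

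If the drug has an acute ECG effect, that effect then sits inside the patient's baseline and is removed from every later change. The primary objective of Part 1 is safety and tolerability, with 4 active patients per cohort (3 in Japan), so a single mis-set baseline can move a cohort mean or suppress a change-based PCSA.

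**Working it through.** The SAP states no figure for this point, so there is none to reproduce. The check applies the rule as written to the Table 4 schedule.

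**Step 1. Which record becomes baseline?** Take a patient with Day 1 ECGs pre-dose and at 2, 4 and 6 hours.

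| Situation | Record selected |
|---|---|
| All times known | Day 1 pre-dose |
| Dose time missing | Day 1, 6 hours post-dose |
| Only the time of the 6-hour record missing | Day 1, 6 hours post-dose |
| Only the time of the pre-dose record missing, rule applied record by record | Day 1 pre-dose |

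**Step 2. Does another rule intervene?** The first-value-of-the-day rule would choose the earlier record, but it excludes ECG at Day 1. Table 4 has a pre-dose window, but that serves time-point summaries and the baseline definition does not refer to it. Section 2.5.5 adds no restriction.

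**Step 3. Effect on a change.** If the acute effect at 6 hours is *e*, each later change in that patient becomes (later − pre-dose) − *e*. Illustration with an assumed *e* = 10 ms, pre-dose QTc 410 ms and 6-hour QTc 420 ms:

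- Later value 425 ms: 425 − 420 = +5 ms, instead of 425 − 410 = +15 ms.
- Later value 471 ms: 471 − 420 = +51 ms, instead of 471 − 410 = +61 ms. The criterion of an increase above 60 ms is then missed.

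**Step 4. Effect on a cohort mean.** With one affected patient on active drug, the mean change shifts by *e* divided by the number of active patients. For an assumed *e* of 5 to 15 ms, the range runs from 5/4 = 1.3 ms (cohort of 4) to 15/3 = 5 ms (Japanese cohort of 3). The SAP gives no value for *e*.

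**Step 5. How much of a repeat-dose effect is removed?** Sections 2.4.4.1 and 2.5.4 equate 7 days with about 5 half-lives, so the half-life is about 7 × 24 / 5 = 33.6 h. With once-daily dosing, accumulation is about 1 / (1 − 2^(−24/33.6)) = 2.6. If effect follows concentration (an assumption), a single-dose effect in the baseline removes about 1/2.6, or roughly 40%, of the steady-state effect at Week 4.

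**Step 6. With the correction.** If post-dose records are barred, the pre-dose ECG is selected in all four situations of Step 1.

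**The case against.** The strongest case against is that the problem is narrow and perhaps rare. Several parts of it stand.

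- **Frequency.** The fallback acts only when a time is missing, and the SAP gives no rate. Table 5 sets Day 1 PK windows as tight as 0h50 to 1h10 after the dose in the same Part 1 patients, so dose times were needed and were probably recorded.
- **Timing.** Section 1 says the earlier SAP versions covering Part 1 were finalised before the Part 1 analyses. New wording now may not reach those outputs.
- **Use.** Section 2.4.5 describes the safety analysis as essentially descriptive, and absolute QTc criteria (above 450, 480 and 500 ms) do not use baseline.

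A reader might also infer more than the SAP supports:

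- **That every parameter is exposed.** Apart from PK, only Part 1 ECGs are shown with same-day post-dose time points. Tables 3 and 6 list Day 2 as their first time point. For other variables the first-value rule, which defaults to the scheduled visit when times are absent, largely covers same-day duplicates.
- **That the error always hides a drug effect.** Placebo patients have none to subtract, and a missing time on the pre-dose record alone need not move baseline.
- **That the whole effect vanishes from later visits.** Under the accumulation argument in the working, part of it remains at Week 4.
- **That pre-dose and post-dose labels are known to be collected.** This is inferred from the time points named in Table 4. The SAP does not say so, and the case report form is not shown.

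None of this changes the central fact: for Day 1 ECGs the rule as written can return a post-dose value, and no other rule corrects it.

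**Conclusion.** The point holds in a limited form and is minor. For a Part 1 patient whose dose time is missing, or whose 6-hour ECG has no time, the written rule makes a post-dose ECG the baseline. On active drug, any acute effect is then subtracted from later ECG changes and change-based PCSAs.

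The reach is the ECG safety summaries of about 27 patients, and within them only those with missing clock times. The number affected is unknown and could be zero. The figures of 5 to 15 ms per patient and 1.3 to 5 ms per cohort mean rest on an assumed effect size and on one affected patient per cohort.

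It would be wrong to read this as a threat to the Part 2 results. Table 6 lists no same-day post-dose ECG, and nothing in the SAP shows an effect on the Part 2 efficacy analyses.

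**What to change.** Add to the fallback in Section 2.1.1:

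- A record identified as post-dose by its scheduled (nominal) time point is never eligible as baseline.
- Where several Day 1 records exist, use the one identified as pre-dose. If none can be identified, use the last value before the date of first dosing.
- Single scheduled Day 1 assessments keep the present date rule, which serves them well.

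The cost is a few lines of text and a small change to the baseline derivation, provided nominal time points are held in the data; that should be confirmed first. For Part 1 outputs already produced, check whether the fallback set any patient's ECG baseline. If it did, correct that patient's changes and change-based PCSAs; if not, record that no output was affected.
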